6.2.4. Tabulation of the Urine ACR Endpoints at Each Assessment Time Point

When tabulating the urine ACR endpoints at each assessment time point, if the date of the visit falls within the allowable time window defined in “Table 6.2: Test/Observation Schedule Allowable Time Windows,” then data that have been collected within a 1-week period that includes the visit day will be used as data for that time point. Also, if the day of the visit at discontinuation falls within the allowable time window of the day of discontinuation in the treatment period and the allowable time window for the time point data, then data that were obtained within a 1-week period that includes the day of the visit at discontinuation will be used as the data for that time point. Data will not be replaced with data from outside the allowable time windows. In addition, if multiple measurements were taken within the allowable time window, then the visit day that was closest to the target date will be used. If the difference (in the number of days) between the day of the measurement and the target day is the same for each of two measurements, then the earlier day will be used.

6.3. Handling of eGFR Data at the End of the Treatment Period (Analysis of 7.6.1.3)

When tabulating eGFR data at the end of the treatment period, the data collected at Week 104 of the treatment period, as defined in “Table 6.2: Test/Observation Schedule Allowable Time Windows” will be used. However, if any data from Week 104 of the treatment period are missing, then these data will be imputed as indicating that an eGFR decline has occurred.

6.4. Handling of Event Endpoint Data

The time to initial event onset (in days)^{*1} and the time to censoring (in days)^{*2} will be used for the event data described in 1 through 14 below.

*1 and *2 are defined in “4.10 Periods of Assessment of Efficacy Endpoint Events.”

1. Composite endpoint of end-stage renal disease (ESRD) onset, doubling of serum creatinine, renal death, and cardiovascular (CV) death
2. Composite endpoint of CV death and hospitalized congestive heart failure
3. Composite endpoint of CV death, non-fatal myocardial infarction, and non-fatal stroke
4. Hospitalized congestive heart failure
5. Composite renal endpoint of end-stage renal disease (ESRD), doubling of serum creatinine, and renal death

6. CV death
7. All-cause death
8. The CV composite endpoint of CV death, non-fatal myocardial infarction, non-fatal stroke, hospitalized congestive heart failure, and hospitalized unstable angina
9. ESRD
10. Doubling of serum creatinine
11. Renal death
12. Non-fatal myocardial infarction
13. Non-fatal stroke
14. Hospitalized unstable angina

6.5. Handling of Clinical Laboratory Values Below and Above the Lower Limit of Quantitation

For values that are at or below the lower limit of quantitation, the lower limit of quantitation will be included in the tabulation. Also, if a measured value has been reported as being below the lower limit of quantitation, a value equal to one-half of the lower limit of quantitation will be included in the tabulation; it will not be considered missing or treated as zero.

For values that are at or above the upper limit of quantitation, the upper limit of quantitation will be included in the tabulation. If a measured value has been reported as being above the upper limit of quantitation*, it will be replaced with a value obtained by adding a 1 to the decimal place after the number of reported digits of the upper limit of quantitation; it will not be considered missing or treated as zero.

*If the upper limit of quantitation is “1000,” and the value is above the upper limit of quantitation, then “1000.1” will be used as the value above the upper limit of quantitation.

7. Statistical Methods

7.1. General Methods

7.1.1. Calculated Descriptive Statistics

The types of descriptive statistics that will be calculated for each continuous data parameter are shown in Table 7-1.

Table 7-1. Types of Descriptive Statistics Calculated

Parameter	Calculated Descriptive Statistics
Descriptive Statistics	Numbers of subjects, mean values, SDs, medians, minimums, maximums

7.1.2. Number of Display Digits

Table 7-2 shows the number of display digits that will be included in the analysis results. Additionally, the digits after the number of display digits will be rounded off (or up), except for the minimum and maximum values.

Table 7-2. Number of Display Digits

Description of Value	Number of Display Digits
p value	Values rounded off to the third decimal place However, if the value is below 0.001, then it will be shown as “< 0.001.”
Odds ratio	To the second decimal place
Proportion (percent)	To the first decimal place
Person-years	To the second decimal place
Hazard ratio	To the second decimal place
Descriptive statistics of measured values and changes therein (mean, SD, median)	To 1 decimal place more than that of the original variable
Descriptive statistics of percent changes (mean, SD, median)	To the second decimal place
Descriptive statistics (minimum and maximum values)	Same as the number of digits of the original variable
LS mean, LS mean SE	To 1 decimal place more than that of the original variable
Geometric Mean, Geometric Mean 95% CI, Geometric LS Mean, Geometric LS Mean 95% CI	To the third decimal place
Ratio of Geometric LS Mean, Ratio of Geometric LS Mean 95% CI	To the third decimal place
Percent change of the endpoint in question (Geometric LS Mean of the ratio of the endpoint in question to the baseline value – 1) x 100	To the first decimal place

7.1.3. Significance Level and Confidence Coefficient

The tests will be all two-sided, with a significance level of 5%. The confidence intervals will be two-sided, and the confidence coefficient will be 95%.

7.2. Subject Disposition

7.2.1. Disposition of the Subjects From Whom Written Consent Was Obtained

Analysis population(s): Subjects who progressed to the run-in period

Analysis parameter(s): Number of subjects who discontinued from the run-in period, number of subjects randomized

Analysis method: For each analysis parameter, the number and proportion of subjects will be tabulated.

Listings

Analysis population(s): Subjects who progressed to the run-in period

7.2.2. Disposition of the Randomized Subjects

Analysis population(s): Randomized subjects

Analysis parameter(s): Number of subjects who completed the treatment period, number of subjects discontinued from the treatment period, reasons for discontinuation from the treatment period, number of subjects who completed the follow-up observation period, number of subjects who discontinued from the follow-up observation period (subjects who were not subjects who completed the follow-up observation period will be tabulated as subjects who discontinued from the follow-up observation period)

Analysis method: For each analysis parameter, the number and proportion of subjects will be tabulated by treatment group.

Listings

Analysis population(s): Randomized subjects

7.2.3. Disposition of Randomized Subjects for Each Analysis Set

Analysis population(s): Randomized subjects

Analysis parameter(s): Number of subjects in the safety analysis set, number of subjects in the FAS, number of subjects in the PPS

Analysis method: For each analysis parameter, the number and proportion of subjects will be tabulated by treatment group.

Listings

Analysis population(s): Randomized subjects

7.3. Demographic and Other Baseline Characteristics

Analysis population(s): FAS, safety analysis set

Analysis parameter(s): See Table 7-3.

Analysis method: The key demographic and other baseline characteristics of each analysis population will be summarized, both overall and by treatment group. For two-value, multivalue, and ordered category variables, the number and proportion of subjects will be tabulated. For

continuous variables, the descriptive statistics will be calculated. Additionally, for the FAS, the values will also be tabulated by eGFR category (eGFR \geq 30 mL/min/1.73 m² and $<$ 45 mL/min/1.73 m², eGFR \geq 45 mL/min/1.73 m² and $<$ 60 mL/min/1.73 m², eGFR \geq 60 mL/min/1.73 m² and $<$ 90 mL/min/1.73 m²) on the first day of the run-in period.

Table 7-3. Investigation of Demographic and Other Baseline Characteristics

Endpoints		Data Category
Sex	Male/Female	Two-value
Age at informed consent (years)		Continuous
Age at informed consent (years)	< 55, \geq 55 and $<$ 65, \geq 65 and $<$ 75, \geq 75	Ordered category
Height (cm)		Continuous
Body Weight (kg)		Continuous
BMI (kg/m ²)		Continuous
BMI (kg/m ²)	< 30, \geq 30	Two-value
Race	Asian (Japanese), Asian (Other), Other	Multivalue
Disease duration of Diabetic Nephropathy		Continuous
Disease duration of Diabetic Nephropathy	< 10, \geq 10, Unknown	Multivalue
Disease duration of Type2 Diabetes		Continuous
Disease duration of Type2 Diabetes	< 10, \geq 10, Unknown	Multivalue
Medical Conditions		
Dyslipidaemia	Yes/No	Two-value
Hypertension	Yes/No	Two-value
Information about the subject's past history of fractures	Yes/No	Two-value
Average number of cigarettes smoked per day		Continuous
Smoking status	Never, Former, Current	Multivalue
eGFR (mL/min/1.73 m ²) on the first day of the run-in period		Continuous
eGFR (mL/min/1.73 m ²) on the first day of the run-in period	\geq 30 and $<$ 45, \geq 45 and $<$ 60, \geq 60 and $<$ 90	Ordered category
eGFR (mL/min/1.73 m ²) on the first day of the treatment period		Continuous
Urine ACR (first morning void urine) (mg/g Cr)		Continuous
Urine ACR (first morning void urine) (mg/g Cr)	\leq 1000, $>$ 1000	Two-value
HbA1c (%)		Continuous
HbA1c (%)	< 7, \geq 7 and $<$ 8, \geq 8 and $<$ 9, \geq 9 and \leq 10, $>$ 10	Ordered category
Fasting blood glucose (mg/dL)		Continuous
Systolic blood pressure (mmHg)		Continuous
Systolic blood pressure (mmHg)	\leq 140, $>$ 140	Two-value
Diastolic blood pressure (mmHg)		Continuous
Diastolic blood pressure (mmHg)	\leq 90, $>$ 90	Two-value
HDL-C (mg/dL)		Continuous
LDL-C (mg/dL)		Continuous
Fasting triglycerides (mg/dL)		Continuous
Fasting urine glucose/creatinine ratio		Continuous

Endpoints		Data Category
(mg/mg Cr)		
Renal function biomarkers eGFRcys, serum cysteine C, erythropoietin, c-peptide, high sensitivity CRP, urine transferrin, NAG, L-FABP, TNFR1, TNFR2		Continuous
eGFRcys (mL/min/1.73 m ²)	< 45, ≥ 45 and < 60, ≥ 60	Ordered category

Listings

Analysis population(s): Randomized subjects

7.4. Concomitant Medications

Analysis population(s): FAS

Analysis parameter(s): Concomitant medications

Analysis method: For both the population overall and by treatment group, the number and proportion of subjects concomitantly receiving ACE inhibitors or ARB drugs will be tabulated for subjects “who have been concomitantly receiving ACE inhibitors or ARB drugs from at least 5 weeks before the start of the screening period,” “who have been concomitantly receiving ACE inhibitors or ARB drugs from at least 4 weeks before the start of the screening period,” “who have been concomitantly receiving ACE inhibitors or ARB drugs from before the day of the first dose,” or for whom the first day of administration of the concomitant medication (before the first day of the run-in period) is the same day as the day of randomization, or earlier.

Listings

Analysis population(s): Randomized subjects

7.5. Status of Treatment Compliance

7.5.1. Duration of Study Treatment in the Treatment Period

Analysis population(s): FAS

Analysis parameter(s): Duration of study treatment (weeks)

Analysis method: Descriptive statistics are presented for the administration duration (in weeks), both overall and by treatment group. The number and proportion of subjects are tabulated by administration duration category.

Treatment duration categories (weeks)

< 13, ≥ 13 and < 26, ≥ 26 and < 52, ≥ 52 and < 78, ≥ 78

Listings

Analysis population(s): Randomized subjects

7.5.2. Treatment Period Treatment Compliance

Analysis population(s): FAS

Analysis parameter(s): Study treatment compliance (%)

Analysis method: Both for the population overall and by treatment group, descriptive statistics will be presented for treatment compliance (%) in the treatment period. The number and proportion of subjects will be tabulated for each of the following treatment compliance (%) categories.

Treatment Compliance (%) Categories

< 75, \geq 75 and < 90, \geq 90 and < 100, =100, > 100

Listings

Analysis population(s): Randomized subjects

7.6. Analysis of Efficacy

7.6.1. Primary Endpoints

7.6.1.1. Primary Analysis

Analysis population(s): FAS, PPS

Analysis parameter(s): Proportion of subjects with a decline of 30% in the eGFR at Week 104 of the treatment period

Analysis method:

In accordance with “6.2.2. Tabulation of the eGFR at Each Assessment Time Point When Imputing Data Outside the Allowable Time Window,” a dataset will be prepared using [REDACTED]. The estimated values from this dataset, and the variance thereof, will be combined using Rubin’s rule, and the proportion of subjects with a decline of 30% in the eGFR at Week 104 of the treatment period, and the 95% confidence interval thereof, will be shown for each treatment group. The point estimate for the difference between the groups (placebo group minus TA-7284 group) and the 95% confidence interval according to the Farrington-Manning method will also be shown.

Listings

Analysis population(s): Randomized subjects

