13.3.2 Efficacy

The following statistical procedure will be used for efficacy. Furthermore, subgroup analyses will be performed for some of the endpoints using stratification factors such as the eGFR (≥ 30 mL/min/1.73 m² and < 45 mL/min/1.73 m²; ≥ 45 mL/min/1.73 m²).

(1) Primary endpoint:

Analysis method for the proportion of subjects achieving a 30% decline in the eGFR

1) Primary analysis

The point estimate for the intergroup difference in the proportion of subjects achieving a 30% decline in the eGFR will be calculated, along with the 95% confidence interval using the Farrington-Manning method.

2) Secondary analysis

An adjusted analysis based on a logistic regression analysis model (with treatment group as a factor) that includes randomization factors as covariates will be performed for the proportion of subjects achieving a 30% decline in the eGFR, and the odds ratio and the 95% confidence interval thereof will be calculated.

Furthermore, in the aforementioned primary and secondary analyses, data will be replaced using a multiple imputation method. Detailed information about, for example, sensitivity analysis will be included in the statistical analysis plan.

(2) Analysis methods for the secondary and other endpoints

1) The Proportion of subjects achieving a 40% decline in the eGFR

An analysis similar to that performed for the proportion of subjects achieving a 30% decline in the eGFR will be performed for the proportion of subjects achieving a 40% decline in the eGFR.

2) Other efficacy endpoints

1. Change and percent change in the eGFR
2. Percent change in the urine ACR (first morning void urine)
3. Change in the HbA1c
4. Change in fasting blood glucose
5. Change in blood pressure (systolic blood pressure, diastolic blood pressure)
6. Change and percent change in lipids (HDL-C, fasting neutral lipids)
7. Change and percent change in body weight
8. Change in the fasting urine glucose/creatinine ratio

The aforementioned outcome measures for the other efficacy endpoints will be evaluated using a mixed model for repeated measures that includes treatment group, baseline value, visit, and treatment group-by-visit interactions. For the urine ACR, furthermore, the log-transformed urine ACR will be used.

3) Event endpoints

1. Composite endpoint of end-stage renal disease (ESRD), doubling of serum creatinine, renal death, and cardiovascular (CV) death
2. Composite endpoint of CV death and hospitalized congestive heart failure

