13.4 Changes Made to Statistical Analysis Plan

If the statistical analysis plan discussed in this section is changed before database lock, the reason for the changes made will be entered in the statistical analysis plan and in the clinical study report. Any analytical procedures changed or added after database lock will be documented along with the reason in the statistical analysis plan and clinical study report and be distinguished from the results of the planned analyses.

14. Protocol Compliance, Deviations, and Changes

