2.3. Randomization Procedures

Subjects will be randomly assigned in a 1:1 ratio to the TA-7284 100 mg tablet group or the TA-7284 tablet placebo group based on stratified randomization, with eGFR on the first day of the run-in period as the stratification factor (≥ 30 and < 45 , ≥ 45 and < 60 , ≥ 60 and < 90).

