An intergroup comparison using a logistic regression model will be performed with a decline of 30% in the eGFR at Week 104 of the treatment period as the target variable, treatment group and the stratification factor eGFR on the first day of the run-in period (≥ 30 and < 45 , ≥ 45 and < 60 , ≥ 60 and $<$

90) as factors, and the urine ACR (first morning void urine) as covariates. Thereafter, the odds ratio of a 30% decline in the eGFR in the TA-7284 group relative to the placebo group at Week 104 of the treatment period, and the 95% confidence interval thereof, will be presented.

Listings

Analysis population(s): Randomized subjects

7.6.1.4. Other Analysis 2

Analysis population(s): FAS, PPS

Analysis parameter(s): Proportion of subjects with a decline of 30% in the eGFR at Week 104 of the treatment period

Analysis method:

The proportion of subjects with a 30% decline in the eGFR at Week 104 of the treatment period, and the 95% confidence interval thereof, will be presented for each treatment group in accordance with “6.2.1 Tabulation by eGFR Assessment Time Point.” The point estimate for the difference between the groups (placebo group minus TA-7284 group) and the 95% confidence interval according to the Farrington-Manning method will also be shown.

Listings

Analysis population(s): Randomized subjects

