9. ESRD
10. Doubling of serum creatinine
11. Renal death
12. Non-fatal myocardial infarction
13. Non-fatal stroke
14. Hospitalized unstable angina

Analysis method:

For the data in “6.4 Handling of Event Endpoint Data,” for each of the endpoint event categories 1 through 14, the number and proportion of subjects experiencing the events in question, as well as the event incidence per 1000 person-years, will be calculated for each treatment group. Kaplan-Meier curves will be presented for each treatment group for endpoint event categories 1 through 8.

Endpoint event categories 1 through 14 will be analyzed using a stratified Cox proportional hazard model in which the baseline hazard is stratified based on the eGFR on the first day of the run-in period (≥ 30 mL/min/1.73 m² and < 45 mL/min/1.73 m², ≥ 45 mL/min/1.73 m² and < 60 mL/min/1.73 m², ≥ 60 mL/min/1.73 m² and < 90 mL/min/1.73 m²), with treatment group included as a factor, and the hazard ratios, 95% confidence intervals, and P values will be presented.

For the endpoint event categories 1 through 14, the number and proportion of subjects experiencing the events in question, as well as the hazard ratios and 95% confidence intervals thereof, will be presented in forest plots for each treatment group.

Listings

Analysis population(s): Randomized subjects

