7.6.3.8. Analyses of Subgroups

The following subgroup analyses will be performed for the analysis described in 7.6.1.1.

Analysis population(s): FAS

Subgroups: Sex (male, female), age (< 65 years, \geq 65 years), disease duration of type2 diabetes (< median in years, \geq median in years), BMI (< 30, \geq 30), HbA1c on the first day of the treatment period (< 8, \geq 8), eGFR on the first day of the run-in period (\geq 30 and < 45, \geq 45

and < 60 , ≥ 60 and < 90), mean of the eGFR on the first day of the run-in period and that on the first day of the treatment period (< 45 , ≥ 45 and < 60 , ≥ 60), urine ACR on the first day of the treatment period (≤ 1000 , > 1000), systolic blood pressure on the first day of the treatment period (\leq median value, $>$ median value)

Analysis parameter(s): Proportions of subjects with declines of 30% and 40% in the eGFR at Week 104 of the treatment period

Analysis method:

In accordance with “6.2.2. Tabulation of the eGFR at Each Assessment Time Point When Imputing Data Outside the Allowable Time Window,” a dataset will be prepared using [REDACTED] by subgroup. The estimates and variances for this dataset will be combined using Rubin’s rule, and the proportions of subjects with declines of 30% and 40% in the eGFR at Week 104 of the treatment period, the point estimates for the differences between the groups (placebo group minus TA-7284 group), and the 95% confidence intervals based on the Farrington-Manning method, will be calculated for each treatment group. These figures, along with the numbers and proportions of subjects in each of these subgroups, will be presented in forest plots.

The following subgroup analyses will be performed for the analysis described in 7.6.2.2 and 7.6.2.3.

Analysis population(s): FAS

Subgroups: eGFR on the first day of the run-in period (≥ 30 and < 45 , ≥ 45 and < 60 , ≥ 60 and < 90)

Analysis parameter(s): Urine ACR (first morning void urine), eGFR, HbA1c, blood pressure (systolic blood pressure, diastolic blood pressure)

Analysis method:

Urine ACR (First Morning Void Urine)

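### Randomisation is stratified by three eGFR levels, but no stratum-weighted risk difference is planned, so the primary interval is conservative to the extent that stratum predicts a 30% decline

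*SAP*

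**What the plan says.** SAP 2.3 allocates patients 1:1 "based on stratified randomization, with eGFR on the first day of the run-in period as the stratification factor", in three levels: 30 to below 45, 45 to below 60, and 60 to below 90.

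Protocol 13.3.2 defines the primary analysis as the between-group difference in the proportion with a 30% eGFR decline, "along with the 95% confidence interval using the Farrington-Manning method". SAP 7.6.1.1 carries this over: estimates from the imputed datasets are combined by Rubin's rule, the difference is placebo minus TA-7284, and "the 95% confidence interval according to the Farrington-Manning method will also be shown". Neither text mentions the strata. The same crude difference is used in SAP 7.6.1.3 and 7.6.1.4, and for the 40% decline in 7.6.2.1.

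The strata are used elsewhere:

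- The logistic models of SAP 7.6.1.2 and 7.6.1.3 take "treatment group and the stratification factor eGFR on the first day of the run-in period" as factors and report odds ratios.
- The full-population repeated-measures models of 7.6.2.2 and 7.6.2.3 include the stratum.
- For the event endpoints, 7.6.2.4 names this method: "stratified Cox proportional hazard model in which the baseline hazard is stratified based on the eGFR on the first day of the run-in period".
- The subgroup section, 7.6.3.8, gives separate differences by eGFR level, with "the 95% confidence intervals based on the Farrington-Manning method".

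**The concern.** Balancing the arms on eGFR removes part of the chance variation in the crude risk difference. A variance formula that ignores the strata still counts that variation, so the interval comes out wider than the design requires. The SAP adjusts for the stratum in its other full-population efficacy models but not in the estimate that carries the primary claim, and the published text gives no reason.

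Precision is what is at stake, in a trial of 150 per arm with a binary primary endpoint. Validity is not. The existing analyses do not fill the gap: an odds ratio is on a different scale, and three subgroup differences are never combined into one estimate.

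**Working it through.** **Inputs from the documents.** 1:1 allocation and three strata (SAP 2.3); 300 patients, 150 per arm (SAP 2.5); two-sided 5% level and 95% intervals (SAP 7.1.3). The rationale for 300 does not appear in the public text, so the sample size cannot be reproduced.

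**Assumptions.** Stratum shares *w* = 35/35/30%, the risks in the table, complete data and exact balance within strata. None of these comes from the documents.

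**Formulas.** Let *p* and *a* be the placebo and drug risks in a stratum, and *P* and *A* their weighted averages.

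- Crude variance: Vc = [P(1−P) + A(1−A)]/150
- Stratified variance: Vs = Σ w[p(1−p) + a(1−a)]/150
- Excess width: √(Vc/Vs) − 1
- Information lost: 300(1 − Vs/Vc) patients
- Power, read as the interval excluding zero, with d = P − A: crude Φ((d − 1.96√Vc)/√Vs); stratified Φ(d/√Vs − 1.96)

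**Direction.** Vc − Vs equals the between-stratum variance of *p* plus that of *a*, divided by 150. This cannot be negative. If stratum sizes are also treated as random, the subtracted term becomes the between-stratum variance of (p + a) divided by 300, which is again never negative. The crude interval can therefore be too wide but not too narrow.

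**One case in full** (placebo 45/25/10%, drug 25/13/5%):

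- P = 0.35×0.45 + 0.35×0.25 + 0.30×0.10 = 0.275; A = 0.0875 + 0.0455 + 0.015 = 0.148; d = 0.127
- Vc = (0.275×0.725 + 0.148×0.852)/150 = 0.32547/150, SE 0.0466
- Vs = [0.35(0.2475 + 0.1875) + 0.35(0.1875 + 0.1131) + 0.30(0.09 + 0.0475)]/150 = 0.29871/150, SE 0.0446
- Variance ratio 1.090; excess width √1.090 − 1 = 4.4%; half-width 9.1 against 8.7 percentage points
- Information lost: 300(1 − 1/1.090), about 25 patients
- Power 78.8% crude, 81.2% stratified: 2.4 points lost

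**All cases**, with simulated coverage from 20,000 trials each (FM is the crude Farrington-Manning score interval, MH the Mantel-Haenszel Wald interval):

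| Placebo risks | Drug risks | SE crude / stratified | Excess width | Patients lost | Power lost (points) | FM coverage | MH coverage |
|---|---|---|---|---|---|---|---|
| 22% flat | 12% flat | 0.0430 / 0.0430 | 0% | 0 | 0 | 95.0% | 94.7% |
| 30/25/20% | 16.5/13.75/11% | 0.0453 / 0.0452 | 0.3% | 2 | 0.2 | 95.1% | 94.7% |
| 30/20/12% | 17/11/6% | 0.0423 / 0.0418 | 1.4% | 8 | 1.0 | 95.5% | 94.9% |
| 45/25/10% | 25/13/5% | 0.0466 / 0.0446 | 4.4% | 25 | 2.4 | 95.9% | 94.6% |
| 55/25/5% | 30/14/3% | 0.0479 / 0.0440 | 8.8% | 47 | 4.4 | 96.5% | 94.4% |

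**Other shares** (20/40/40% to 50/30/20%). At 45/25/10% the excess width is 3.8% to 4.6% and the power loss 1.6 to 2.7 points. At 55/25/5% the power loss is 2.3 to 5.9 points.

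**Separate check** (equal thirds, overall risks 25% and 15%, 200,000 trials per case). With allocation balanced within strata, crude coverage was 95.1% with no gradient, 95.1% for placebo risks 30/25/20%, 95.7% for 40/25/10% and 96.6% for 50/20/5%. Under simple randomisation it stayed at 94.9% to 95.1%, so the over-coverage comes from the stratified allocation. With gradients running in opposite directions in the two arms, the excess width was only 0.1%.

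**Effect of imputation.** Add the same between-imputation variance B to both variances in the 45/25/10% case (Vc = 1.09, Vs = 1). If B is 10% of the crude total, B = 1.09×0.1/0.9 = 0.121, and √(1.211/1.121) − 1 = 3.9%. If B is 20%, B = 0.2725, and √(1.3625/1.2725) − 1 = 3.5%.

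**The case against.** The best defence is that a simple marginal difference, named in the protocol and implemented faithfully in the SAP, is a legitimate primary analysis. An adjusted logistic model is already planned for the same endpoint, and differences by stratum will be shown. All of that is true, and it is why this is not an error.

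The size is also unknown. The endpoint is a percentage decline from the patient's own baseline, so a steep gradient by baseline eGFR cannot be presumed. The larger figures need a 4.5-fold or 11-fold range of placebo risk across strata. Details of the allocation procedure and the imputation method are not in the public text, so exact balance and the size of the imputation effect are assumptions. The primary section names no test, so the power figures apply only to a reading of whether the interval excludes zero. These limits stand.

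Two arguments carry less weight. The Mantel-Haenszel Wald interval does cover slightly below 95%, but with an n−1 variance its coverage was about 94.8% to 95.0%, so the shortfall is trivial. A supportive analysis would leave the primary interval as wide as before, but it would still supply the missing estimate on the primary scale without departing from the protocol.

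**Conclusion.** The point holds as an optional efficiency improvement. The trial stratifies on eGFR, and no planned analysis gives one risk difference that uses the strata. The crude interval is valid and never too narrow.

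The loss is nil for flat risk, 0.3% to 1.4% of interval width for gentle gradients, about 4% for a strong gradient and close to 9% for an extreme one, all before dilution by imputation. These sizes rest on assumed shares and risks, balance within strata and complete data. The direction does not depend on the particular shares or risks. Confidence in the practical importance is medium, because the documents give nothing from which to judge how strongly stratum predicts the endpoint.

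**What to change.** Before database lock, amend SAP 7.6.1.1 and 7.6.2.1 so that the risk difference is stratified by the three randomisation levels in each imputed dataset, for example as a Mantel-Haenszel difference with its variance, and pooled by Rubin's rule. That method yields the estimate and variance that Rubin's rule needs. Do the same on the single datasets of 7.6.1.3 and 7.6.1.4, and keep the crude Farrington-Manning interval as supportive.

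Record the change and its reason in SAP section 9. Protocol 13.4 allows this: for changes before lock, "the reason for the changes made will be entered in the statistical analysis plan and in the clinical study report". If the sponsor prefers not to replace the method named in Protocol 13.3.2, add the stratified difference as a pre-specified supportive analysis. If the database is already locked, Protocol 13.4 requires any addition to be documented with its reason and kept apart from the planned results.

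The cost is SAP wording and a little programming, since the stratum is known for every patient. Replacing the primary method also means a documented departure from the protocol and, with the plain Wald form, coverage slightly under nominal.
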